**Table 7 Dose Exploration Schema Belantamab mafodotin in combination with GSK'998 (aOX40)**

Dose level	Belantamab mafodotin dose	GSK'998 (aOX40) dose
1 (starting dose level)	1.9 mg/kg	8 mg
2	2.5 mg/kg	8 mg
3	2.5 mg/kg	24 mg

**4.2. Scientific Rationale for Study Design****4.3. Justification for Dose**

GSK'998 (aOX40) will initially be administered at a flat dose of 8 mg IV Q3W on Day 1 of each 21-day cycle after the infusion with belantamab mafodotin. Please refer to 208887 MP Section 4.3 for starting dose of belantamab mafodotin.

Previous clinical experience for GSK'998 (aOX40) in Study 201212 [NCT02528357] was based on weight-proportional dosing. The 8 mg dose to be tested in this study is considered equivalent to the 0.1 mg/kg dose in the ongoing FTIH trial [NCT02528357], assuming a median participant weight of 80 kg.

The 8-mg dose of GSK'998 (aOX40) is considered an appropriate dose for combination therapy with belantamab mafodotin based on the following: According to currently available data, the starting dose of 8 mg was well tolerated and did not result in excessive toxicity in advanced solid tumor patients. Doses up to 10 mg/kg (800 mg equivalent) GSK'998 (aOX40) monotherapy tested in the ongoing FTIH trial [NCT02528357] did not result in DLTs and an MTD was not established. To date, there is no apparent dose-toxicity response with GSK'998 monotherapy. The starting dose of 8 mg results in exposure approximately 100-fold lower than the 10 mg/kg dose.

In the ongoing FTIH trial in participants with advanced solid tumors [NCT02528357] the GSK'998 dose level of 0.1 mg/kg (equivalent to 8 mg) represents one dose level below the dose (0.3 mg/kg, equivalent to 24 mg) that demonstrated linear PK, saturation of peripheral OXO40 RO across the dosing interval, and clinical activity. No clinical activity was observed for GSK'998 monotherapy 0.1 mg/kg in participants with solid tumors; however, evidence of some pharmacological target engagement was observed, with ~30% RO by Week 3 post-dose compared ~85% RO for the 0.3 mg/kg dose level. GSK'998 0.1 mg/kg trough plasma concentrations dropped below the level of quantification by Week 3, whereas 0.3 mg/kg trough concentrations remained measurable. Thus, an 8 mg (0.1 mg/kg equivalent) dose of GSK'998 is considered to balance appropriate tolerability with the potential for exposing participants to subtherapeutic doses.

Based on the large capacity, non-specific clearance, and recycling mechanisms for mAbs, no DDI related to non-specific IgG turnover is expected between belantamab mafodotin and GSK'998 (aOX40) for the dose ranges considered.

Because the ligands of belantamab mafodotin and GSK3174998 are expressed on different target cell populations, no DDI related to target mediated disposition is expected between belantamab mafodotin and GSK'998 (aOX40).

The safety profiles of both antibodies currently do not suggest overlapping toxicity.

Therefore, a starting dose of 8 mg (0.1 mg/kg equivalent) IV Q3W is anticipated to be well tolerated without excessive, treatment-related toxicity in this RRMM participant population.

#### **4.4. Participant Completion and End of Study Definition**

There is no change in this section from the 208887 MP.

##### **4.4.1. Participant Completion Definitions:**

A participant is considered to have completed the study if they received at least 1 cycle of combination study treatment, and the participant is followed until death (even after starting a new anti-cancer treatment) or until the end of the study.

##### **4.4.2. Study Completion:**

Sub-study completion: For the DE and CE phases, a sub-study is considered to have completed if all participants have been followed up for 36 months, withdrawn consent, are lost to follow up, or died. A sub-study may close after or during DE for safety or tolerability reasons or if an insufficient number of responders have been observed.

The end of study (EOS) is the last visit of the last participant in the last sub-study. This will occur when the last participant has been followed up for 36 months, died, withdrawn consent or is lost to follow-up. Any patient who has not reached PD at this time will be treated in a separate study roll over study or at the investigators' discretion.

## **5. STUDY POPULATION**

Please refer to the 208887 MP for the overall planned Study Population details for the study.

Information and details specific to Sub-study 1 are in Section 5.2 below.

Participants are eligible to be included in the study only if all of the criteria in Section 5.2, and in 208887 MP Section 5.1 and Section 5.2 apply. Prospective approval of protocol deviations to recruitment and enrollment criteria, also known as protocol waivers or exemptions, is not permitted.

## **5.1. Inclusion Criteria for Participants**

There are no additional inclusion criteria for Sub-study 1.

## **5.2. Exclusion Criteria**

Participants are excluded from the study if any of the following criteria apply:

The exclusion criteria #26 and #27 below are in addition to the exclusion criteria already defined in 208887 MP Section 5.2.

26. Autoimmune disease (current or history) or syndrome that required systemic treatment within the past 2 years. Replacement therapies which include, physiological doses of corticosteroids for treatment of endocrinopathies (for example, adrenal insufficiency) or treatment of hypothyroidism is allowed on study.
27. In addition, exclusion for a recent (within the past 6 months) history of symptomatic pericarditis.

## **5.3. Lifestyle Considerations**

## **5.4. Screen Failures**

# **6. STUDY INTERVENTION**

Please refer to the 208887 MP for the overall Study Intervention for the study.

Information and details specific to Sub-study 1 are in Section 6.1, Section 6.2 and Section 6.6 below.

Study intervention is defined as belantamab mafodotin administered with GSK'998 treatment and administered to a study participant according to the study protocol.

## 6.1. Study Intervention(s) Administered

Specifications for belantamab mafodotin and GSK'998 IP in this study are given (Table 8).

**Table 8 Belantamab mafodotin and GSK'998**

Intervention Name	Belantamab mafodotin	GSK'998 (OX40)
Type	Drug	Drug
Dose Formulation	Powder for solution for infusion	Powder for solution for infusion
Unit Dose Strength(s)	100 mg/vial	40 mg/vial
Route of Administration	Delivered as IV solution, infused over 30-60 minutes	Delivered as IV solution over 30 minutes
IMP	GSK2857916 ( belantamab mafodotin )	GSK3174998
Sourcing	GSK	GSK
Packaging and Labelling	Study Intervention will be provided in vials. Each vial will be labeled as required per country requirement.	Study Intervention will be provided in vials. Each vial will be labeled as required per country requirement.

## 6.2. Administration of Belantamab mafodotin and GSK'998

- Belantamab mafodotin will be administered before administration of GSK'998 (aOX40).
- GSK'998 (aOX40) will be administered via IV infusion on D1 of every 21 day cycle
- Belantamab mafodotin will be administered to subjects intravenously as mg/kg calculated dose at the study site. The dose to be administered is based on actual body weight calculation and may be reduced for toxicity according to protocol guidelines.
- Administration will be documented in the source documents (208887 MP Section 12.1.8) and reported in the eCRF. The time of start and end of infusion will be documented in eCRF.
- Belantamab mafodotin (Section 6.1) will be administered on Day 1 of each cycle at the assigned dose as an IV infusion. Premedication is not required prior to infusion unless deemed medically necessary by the investigator, in which case it should be administered according to institutional recommendations. In case of infusion related reactions related to belantamab mafodotin the rules outlined in 208887 MP Section 7.1.6 and Section 11 should be followed.
- After the infusion of belantamab mafodotin has been completed subjects will be required to enter at least 1-hour rest period before starting GSK'998 (aOX40) infusion where appropriate.
- The intended cycle time of GSK'916 BCMA as a monotherapy is 21 days (+3-day window) and cannot occur more frequently than this.

**Table 9 Route of Administration and Dose Timing for Belantamab mafodotin and GSK'998 in the DE phase**

	Belantamab mafodotin	GSK'998 (aOX40)
Route of administration	IV infusion (see Section 6.1 for details)	IV infusion (see Section 4.1 for details)
Timing	Administer first, on day 1 of 21 day cycles	Start 1 h after belantamab mafodotin EOI on day 1 of 21 day cycles. For guidance about dosing if an infusion related reaction (IRR) occurs please see 208887 MP Section 11.

Participants enrolled in the DE phase and the CE phase will be treated until disease progression, intolerable toxicity, informed consent withdrawal, the end of the sub-study, study or death.

### 6.3. Preparation/Handling/Storage/Accountability

### 6.4. Measures to Minimize Bias: Randomization and Blinding

### 6.5. Concomitant Therapy

### 6.6. Dose Modification

Dose modification is for Belantamab Mafodotin when in Combination with GSK'998. For information related to overall dose modification refer to the 208887 Master Protocol. Also see 208887 MP Section 11 for guidelines on dose modification and management of events for belantamab mafodotin and other partner combination treatments.

#### 6.6.1. Permitted Dose Reductions for Belantamab Mafodotin when in combination with GSK'998

- For further details regarding dose modifications see Section 6.6 for belantamab mafodotin and 208887 MP Section 11.

**Table 10 Permitted dose reductions for Belantamab mafodotin when in combination with GSK'998 (aOX40)**

Belantamab mafodotin Dose Level	1st Dose Reduction
2.5 mg/kg	1.9 mg/kg
1.9 mg/kg	-

- The dose of GSK'998 (aOX40) will not be modified. Please refer to Section 2.3.
- If the participant cannot tolerate the drug after the allowed dose reductions, he or she must be withdrawn from the study for lack of tolerability.
- Only one dose reduction of belantamab mafodotin (to 1.9 mg/kg) is permitted from any 2.5 mg/kg belantamab mafodotin dose level in Table 10.

- No dose reduction of belantamab mafodotin is permitted from the starting dose level of 1.9 mg/kg as lower doses are likely to be inefficacious based on findings from Part 1 of the FTIH trial (GSK Study BMA117159).
- In case of full resolution of symptoms which lead to dose reduction, further treatment with belantamab mafodotin at the initially-assigned dose may be considered by the investigator.
- Resuming treatment with belantamab mafodotin may be possible after the toxicity has resolved to Grade 1 or less.
- If GSK'998 (aOX40) is permanently withdrawn the participant can remain on belantamab mafodotin, if belantamab mafodotin is permanently withdrawn the participant will be withdrawn from all study treatment.

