Physical Exam	X		X		
 
EoT visit safety assessments to occur within 30 days from the last dose, or prior to the new anti-MM treatment (whichever occurs first).
 
PFS follow-up every 21 days (<math>\pm 7</math> days) for participants who discontinue IP for a reason other than PD. Disease evaluations will continue until confirmed PD, death, start of a new anticancer treatment, withdrawal of consent, or end of the study whichever occurs first. Once participant progresses, move to OS Follow-up.
 
The survival for MM will be documented in medical charts. No visit necessary. Contacts will be made via phone calls, emails or other means of communications every 12 weeks (<math>\pm 14</math> days) until end of study. Participant does not need to come in for visit unless they are being followed for corneal signs that are present at the end of study treatment.
 
AEs/SAEs will be collected up to 70 days after the last dose of study treatment and immune-related AEs/SAEs will be collected up to 90 days post last dose. All SAEs related to study participation (e.g., protocol mandated procedures, tests, or change in existing therapy) are to be collected from consent through OS follow-up. All AE's/SAE's will be followed until the event is resolved, stabilized, otherwise explained, or the participant is lost to follow-up.
 
End of treatment ophthalmic exam to be performed by a qualified eye-care specialist. See 208887 MP Section 8.2.7 for list of exams.
 
Participants with a treatment-related change in vision at the End of Treatment Visit will be followed every 6 weeks (<math>\pm 7</math> days) until return to baseline, deemed clinically stable by the eye-care specialist, or up to 12 months (whichever comes first). Clinically stable is defined as changes <math>\leq</math> Grade 1. See 208887 MP Section 8.2.7 for list of exams
 
CBC may be done more frequently as clinically indicated. Refer to 208887 MP Appendix 2 for comprehensive list of lab tests.
 
Final pregnancy test (serum or urine) must be performed in women of childbearing potential 90 days (<math>\pm 7</math> days) after last dose of study treatment. For
 
	
Vital Signs (BP, HR, Body Temperature)	X		X			
Adverse Events	X 		Related SAEs only 	Related SAEs only 		
Concomitant Medications	X		X			
Safety						
Ocular Exam	X 		X 	X 		

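### Section 6.6.1 withdraws participants who cannot tolerate belantamab mafodotin from the study, while Table 5 keeps those who stop treatment without progression in follow-up

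*Protocol*

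**What the plan says.** Table 10 in Protocol Section 6.6.1 allows one reduction of belantamab mafodotin, from 2.5 to 1.9 mg/kg. At the lower level, "No dose reduction of belantamab mafodotin is permitted from the starting dose level of 1.9 mg/kg". The second bullet under the table then says that a participant who still cannot tolerate the drug "he or she must be withdrawn from the study for lack of tolerability". The last bullet of the same list, on permanent stopping of either agent, says that "if belantamab mafodotin is permanently withdrawn the participant will be withdrawn from all study treatment".

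Elsewhere the module treats the same event as the end of treatment:

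- The text after Table 9 in Section 6.2 says that participants "will be treated until disease progression, intolerable toxicity, informed consent withdrawal, the end of the sub-study, study or death".
- Table 5, note 2, schedules progression follow-up every 21 days "for participants who discontinue IP for a reason other than PD".
- Table 5, note 4, collects AEs and serious AEs to 70 days after the last dose, and "immune-related AEs/SAEs will be collected up to 90 days post last dose".
- Table 5, note 6: "Participants with a treatment-related change in vision at the End of Treatment Visit will be followed every 6 weeks", for at most 12 months, stopping earlier on return to baseline or clinical stability.
- Table 5, notes 17 and 18, take one ADA sample and one PK sample for GSK'998 at least 8 weeks after the last dose.

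**The concern.** The second bullet is mandatory and names the study, not the treatment. A site that obeys it would close follow-up for a participant whom Table 5 requires it to keep seeing.

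The participants concerned are those who stopped for toxicity. Safety and tolerability is the primary objective of dose exploration (SAP Section 1.2, Table 2). AEs of special interest, ocular findings and ADAs are secondary endpoints. Follow-up lost under this rule would therefore be missing for a reason tied to what is being measured. A participant who leaves with unresolved eye toxicity could also lose scheduled examinations, which is a patient-safety matter whatever is analysed.

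**Working it through.** No figure in the plan needs reproducing. The check is a comparison of texts, followed by simple arithmetic on what a literal reading would remove.

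**1. Which drug.** The bullet applies after the allowed reductions. Only belantamab mafodotin has one (Table 10), and Section 6.6.2 permits no dose modification of GSK'998. So the drug in question is belantamab mafodotin.

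**2. What Table 5 does with the same participant.** Note 2 covers every non-progression reason for stopping, which includes toxicity. It ends disease evaluations at confirmed progression, death, new anticancer therapy, withdrawn consent or end of study. Intolerance is not on that list. Section 6.2 likewise names intolerable toxicity as ending treatment. Both conflict with removal from the study.

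**3. The two bullets in Section 6.6.1.** The last bullet speaks of study treatment and the second of the study. Leaving the study also means leaving treatment, so a site can obey both. This is inconsistent wording, not a strict contradiction. The conflict rests on Table 5 and Section 6.2.

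**4. Follow-up removed per affected participant.** The windows come from note 4. The follow-up columns of Table 5 themselves show only related serious AEs, with note 4 attached, and I take the note as governing. Note 1 says "EoT visit safety assessments to occur within 30 days from the last dose", so day 30 is the latest such visit. Days lost = window − day of withdrawal, counted from the last dose.

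| Withdrawn at | AEs, 70-day window | Immune-related, 90-day window |
|---|---|---|
| Next due dose, day 21 | 70 − 21 = 49 days; 49/70 = 70% | 90 − 21 = 69 days; 69/90 = 77% |
| End-of-treatment visit, day 30 | 70 − 30 = 40 days; 40/70 = 57% | 90 − 30 = 60 days; 60/90 = 67% |
| After a hold longer than 90 days | 0 | 0 |

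The last row is possible because Section 6.6.2 allows a delay of 16 weeks, which is 16 × 7 = 112 days.

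**5. Late samples.** Eight weeks is 8 × 7 = 56 days, so neither the ADA nor the PK sample is due at day 21 or day 30. Both would be missed.

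**6. Eye examinations.** At one every 6 weeks for 12 months, 365/42 = 8.7, so up to 8 examinations. This applies only if there is a treatment-related vision change at end of treatment that neither returns to baseline nor stabilises.

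**7. Reach.** SAP Section 5 gives 6 participants at Dose Level 1 and 3 at Dose Level 2, so 6 + 3 = 9. Neither document says how many stopped for intolerance, so the range is 0 to 9.

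**The case against.** The strongest reply is that this is a slip of the pen. The sentence sits in a dose-reduction list, and Section 6.2 and Table 5 show what was meant. Rules on discontinuation and withdrawal (Section 7) are deferred to the Master Protocol, which may separate stopping treatment from leaving the study. Note 4 of Table 5 also requires every AE to be followed until it settles, is accounted for or the participant cannot be traced.

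Most of this stands. The wording is probably loose, and what a withdrawn participant would still undergo depends partly on text not supplied. It does not clear the sentence, because the conflict with Table 5 lies inside this module and the instruction is phrased as an obligation. The note 4 rule covers events already under way. It does not replace collection of new ones.

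The other side is also right about consequences. Enrollment is closed, and SAP Table 2 has no progression-free or overall survival endpoint. SAP Section 4.5 reports on-treatment AEs unless stated otherwise, so late events may not enter those tables. That depends on the Master SAP, also not supplied.

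A reader might infer three stronger things that the documents do not support:

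- *That Sections 4.4.1, 4.4.2 and the Section 7 heading are also contradicted.* Section 4.4.1 defines a completer, and a withdrawn participant is simply not one. Section 4.4.2 defines completion of a sub-study and the study. A heading is not a rule.
- *That at 1.9 mg/kg the rule applies at the first toxicity.* Sections 6.6.1 and 6.6.2 allow holding the dose and resuming once toxicity falls to Grade 1 or less. Intolerance is a judgement made after that option.
- *That one missed late event could move the overall AE rate.* A participant withdrawn for intolerance already has an AE and is already counted. A shift from 0/9 (exact 95% upper limit 33.6%) to 1/9 (11.1%, upper limit 48.2%) could arise only for a specific event type not otherwise seen.

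**Conclusion.** The point holds as an inconsistency between a mandatory sentence in Section 6.6.1 and the follow-up set out in Table 5 and implied by Section 6.2. It is worth correcting but is not a major defect.

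On a literal reading, an affected participant loses 57% of the AE window and 67% of the immune-related window if withdrawn at a day-30 visit. Across the cases shown, the loss runs from nothing to 70% and 77% respectively. The late ADA and PK samples and up to 8 eye examinations may also go.

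These figures assume that withdrawal from the study ends all scheduled assessments, which the Master Protocol could qualify. There is no evidence that anyone was withdrawn under this sentence, and the effect on the SAP's on-treatment summaries may be small or nil. The conflict in the text is certain; its practical effect is not.

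**What to change.** First check the current protocol. The SAP is based on Protocol Amendment 5 (21 January 2022), while the module reviewed here is Amendment 4, so the sentence may already have been corrected.

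If it has not, replace "he or she must be withdrawn from the study for lack of tolerability" in the second bullet under Table 10 with: *must permanently discontinue all study treatment for lack of tolerability and continue follow-up per Table 5 unless consent is withdrawn*. This also brings the bullet into line with the last one in the list.

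The cost is one sentence. Table 5 already schedules the assessments, so none is added and the SAP does not change. With enrollment closed, the correction matters only for participants still on treatment or in follow-up at either dose level.

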#### **6.6.2. Permitted Dose Modifications of GSK'998 when in combination with Belantamab mafodotin**

There are no dose modifications allowed for GSK'998 (aOX40). Fixed (flat) dosing of GSK'998 (aOX40) will be used during the study for all participants receiving GSK'998 (aOX40), regardless of participant weight.

Dosing of GSK'998 (aOX40) may be delayed **if needed, but this will not affect the dosing schedule for belantamab mafodotin**. GSK'998 may only be administered with GSK'916 with the possibility of GSK'998 administration 1 day later than GSK'916 in the case of an IRR on the date of GSK'916 infusion. The maximum treatment delay to GSK'916 treatment is 16 weeks and therefore the maximum treatment delay to GSK'998 is 16 weeks +1 day, unless agreed in writing by the Medical Director. Please refer to 208887 MP Section 11 for details on management of adverse events requiring delay or discontinuation of GSK'998 (aOX40) dosing.

**If belantamab mafodotin is delayed for any reason, then GSK'998 (aOX40) will also be delayed.**

If participants develop toxicity which would preclude additional dosing with GSK'998 (aOX40), they can continue with belantamab mafodotin only. For drug-related toxicities not listed in these tables, the general rule of withholding the dose for Grade  $\geq 3$  toxicity should be followed. Resuming treatment will be possible with or without dose reduction after the toxicity has resolved to Grade  $\leq 1$  and with agreement between the principal investigator (PI) and GSK Medical Director.

Investigators must contact the GSK Medical Director for all Grade  $\geq 3$  clinically significant non-hematological drug-related toxicities where interruption or permanent discontinuation of study treatment may be warranted according to the guidelines provided in 208887 MP Section 11. Otherwise, investigators are encouraged to contact the GSK Medical Director as needed to discuss any case that warrants separate discussion outside of the scope of current guidelines.

## **7. DISCONTINUATION OF STUDY INTERVENTION AND PARTICIPANT WITHDRAWAL FROM THE STUDY**

Please refer to the 208887 MP for the information contained in the Level 2 headings below.

- 7.1. Discontinuation of Study Intervention**
- 7.2. Participant Withdrawal from the Study**
- 7.3. Lost to Follow Up**

